6 STUDY DESIGN

6.1 DESCRIPTION OF THE STUDY

ACT14132 is a multi-stage, phase 2, open-label, multicenter, multinational, ascending dose cohort, repeated intravenous (IV) infusion study of avalglucosidase alfa in pediatric patients with IOPD who have been previously treated with alglucosidase alfa and demonstrated clinical decline (Stage 1) or sub-optimal clinical response (Stage 2) in specified respiratory function, motor skills, cardiac parameters, and/or new onset of ptosis.

Stage 1

- Cohort 1 – at least 5 IOPD patients will receive avalglucosidase alfa at 20 mg/kg qow for 6 months.
- Cohort 2 – at least 5 IOPD patients will receive avalglucosidase alfa at 40 mg/kg qow for 6 months.

Stage 2

- Cohort 3 – at least 10 IOPD patients will be randomized 1:1 to receive avalglucosidase alfa at the highest tolerated avalglucosidase alfa dose in Stage 1 (20 mg/kg qow or 40 mg/kg qow) or alglucosidase alfa treatment at current stable dose (defined by dose of alglucosidase alfa administered regularly for a minimum of 6 months immediately prior to study entry) for 6 months. The randomization will be stratified on gender.

The first 5 patients will be enrolled in the 20 mg/kg qow dose cohort. If determined safe by an independent DMC after the 3rd patient in the 20 mg/kg qow group (Cohort 1) has received the 3rd infusion of avalglucosidase alfa and after 5 patients have started treatment in Cohort 1, the next cohort of avalglucosidase alfa at higher dose (40 mg/kg qow) will be initiated (Cohort 2). Cohort 3 will be initiated after determination of the highest tolerated avalglucosidase alfa dose in Cohort 1 and Cohort 2 after at least 5 patients in Cohort 1 and at least 5 patients in Cohort 2 have received the 7th dose of avalglucosidase alfa (or completed Week 13 with a minimum of 6 infusions).

After completion of treatment for 6 months (Week 25) and data collection for the principal analysis, the patients will continue on long-term avalglucosidase alfa treatment and follow-up in the Extension Period for up to a total of 7 years in the study. Cohort 3 patients receiving alglucosidase alfa will have the option to switch to treatment with avalglucosidase alfa in the extension period or discontinue the study. The data cut-off for the primary analysis will be after the last patient in Cohort 3 has completed 6 months of treatment (Week 25).

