11.5 INTERIM ANALYSIS

While all patients will be followed for up to 7 years during the study, the primary analysis for the study will be performed when all Cohort 3 patients have completed the 6-month PAP. In addition, safety analyses will be performed in multiple time points by DMC (see [Section 6.4.1](#)) to determine the dose for next cohort and the MTD.

After the primary analysis for the PAP, interim analyses may be performed during the extension period to provide additional information for regulatory purpose.

Since there is only one hypothesis test for the composite score to be performed at the end of the PAP, no adjustment is needed for the interim analyses.

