After completion of treatment for 6 months (Week 25) and data collection for the primary analysis, the patients will continue on long-term avalglucosidase alfa treatment and follow-up in the Extension Period for up to a total of 3 years in the study. Cohort 3 patients receiving alglucosidase alfa will have the option to switch to treatment with avalglucosidase alfa maximum tolerated dose (MTD) as determined based on safety data from both dose levels in Cohort 1 and Cohort 2 in the extension period or discontinue the study. The data cut-off for the primary

analysis will be after the last patient in Cohort 3 has completed 6 months of treatment (Week 25) and analysis will be conducted on all data available by then.

Safety, efficacy, PK and [REDACTED] will be performed at scheduled visits throughout the study treatment period. Ventilator use, adverse events (AEs) and concomitant and pre-infusion medications/therapies will be monitored continuously throughout the study.

If a patient in Cohort 1, receiving 20 mg/kg qow avalglucosidase alfa, experiences further clinical decline at or after Week 25 when compared to prior to enrollment in ACT14132, and as defined by more rapid worsening of criteria of clinical decline, which is sustained on repeated study assessments, the patient may be managed per the discretion of the Investigator, which may include return to treatment with commercially available alglucosidase alfa (and termination of study participation) or increasing the avalglucosidase alfa dose to 40 mg/kg qow or MTD, once established, while being enrolled in the extension period of the study.

If a patient in Cohort 2 or 3 experiences further clinical decline at or after Week 25 as defined by more rapid worsening of criteria of clinical decline than prior to study start, which is sustained on repeated study assessments, the patient may be managed per the discretion of the Investigator. This may include return to treatment with commercially available alglucosidase alfa (and termination of study participation).

Patients must have completed the 25-week treatment period of the study before dose increase of avalglucosidase alfa (or start of avalglucosidase alfa for patients receiving alglucosidase alfa in Cohort 3) will be considered.

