1.4 STUDY PLAN

For each patient who signs the informed consent, the study consists of:

- An up to 14-day screening period (may be extended to up to 4 weeks in pre-specified situations [refer to protocol Section 10.1.1]);
- A 25-week treatment period (Primary Analysis Period [PAP]);
- An up to 120-week Extension Treatment Period (ETP);
- An up to 4-week post-treatment observation period.

Figure 1 – Graphical Study Design

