2 STATISTICAL AND ANALYTICAL PROCEDURES

The interim analysis will be performed when all Cohort 3 patients have completed the 6-month (25 weeks) primary analysis period and will include a formal database lock and analyses of safety (including adverse events, physical examinations and growth, clinical laboratory evaluations, electrocardiogram [ECG], vital signs and immunogenicity), PK, efficacy (including GMFM-88, GMFCS-E&R, Pompe-Pediatric Evaluation of Disability Inventory [PEDI] mobility, Quick Motor Function Test [QMFT], echocardiography [ECHO], Eyelid position measurements including Interpalpebral fissure distance [IPFD], Margin reflex distance-1 [MRD-1], Margin pupil distance [MPD], total creatine kinase [CK], CK with MB fraction, and Composite Score Constructed Considering 3 Domains: GMFM-88 and GMFCS-E&R, Ptosis, and Respiratory Function), PD (urinary Hex4 level), and exploratory effect of avalglucosidase alfa treatment on functional endurance, six-minute walk test (6MWT), respiratory function (including Pulmonary Function Testing [PFT] and ventilator use diary), PedsQL Generic Core Scales, HRQOL, pain (including PedsQL Pediatric Pain Questionnaire and Visual Analogue Scale [VAS]), developmental disability (including Bayley Scale of Infant and Toddler Development, Third Edition [Bayley-III] and Leiter International Performance Scale, Third Edition [Leiter-3]), and hearing testing in patients with IOPD. A Clinical study report (CSR) will be prepared after the PAP analysis.

After the completion of primary analysis when all Cohort 3 patients have completed the 6-month (25 weeks) primary analysis period, interim analyses may be performed in ETP to provide additional information for regulatory purpose.

The final ETP analyses will be performed after all patients completed ETP. A final DBL will occur and a final CSR will be prepared after the ETP analyses.

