- During the 25-week treatment period, pre-infusion samples from patients receiving avalglucosidase alfa will be collected every month for evaluation of anti-avalglucosidase alfa ADA and every 3 months for evaluation of anti-alglucosidase alfa ADA. In addition, samples will be collected at Visit 3 (Day 8) to monitor for an early antibody response using both assays. For patients receiving alglucosidase alfa, only anti-alglucosidase alfa ADA will be evaluated.
- During the 120-week extension period, pre-infusion samples from all patients will be collected every 3 months for evaluation of anti-avalglucosidase alfa ADA and every 6 months for evaluation of anti-alglucosidase alfa ADA. In addition, participants in Cohort 3 switching to avalglucosidase alfa will have samples collected at Visit 17 (Week 28) to monitor for an early antibody response using both assays, followed by collection every month for 6 months and then every 3 months for evaluation of anti-avalglucosidase alfa ADA.
- ADA seropositive patient serum will be assessed for neutralizing antibodies (NAbs) to avalglucosidase alfa and/or alglucosidase alfa, as appropriate, including inhibition of enzyme activity and uptake.

Samples may be collected from patients and evaluated for anti-drug IgE, complement activation, serum tryptase following moderate, severe, or recurrent mild IARs suggestive of hypersensitivity reactions.

In the event a patient exhibits signs or symptoms suggestive of systemic immune complex mediated reactions involving skin and other organs, serum samples are obtained for the evaluation of circulating immune complexes.

The qualitative sample status of the ADA will be assessed and be categorized into the following classes:

- ADA-negative sample: a sample is considered negative if ADAs are not detected (i.e., negative in screening assay or reactive in screening but negative in confirmatory assay).
- ADA-positive sample: sample in which ADA is detected (i.e., sample generates an assay signal equal to or greater than the cut-point in the screening assay and is tested positive in the confirmatory assay).

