3 INTERIM ANALYSIS

While all patients will be followed for up to 3 years during the study, the primary analysis for the study will be performed when all Cohort 3 patients have completed the 6-month PAP or discontinued from the study before completing PAP. In addition, safety analyses will be performed in multiple time points by the DMC to determine the dose for next cohort and the MTD. The DMC procedures are detailed in the DMC charter. Furthermore, an additional analysis might be performed for alglucosidase alfa submission.

Since there is only one hypothesis test for the composite score to be performed at the end of the primary analysis period, no adjustment is needed for the interim analyses. Additional analyses after PAP will be considered for supportive purpose.

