4 DATABASE LOCK

The DBL for the primary efficacy analyses is planned to be approximately 30 days after last patient last visit in PAP.

The final database lock for the study is planned to be approximately 30 days after the last patient last visit in ETP.

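### The SAP's extension period and efficacy windows stop at Week 145 although the protocol continues for up to 226 more weeks; separately, protocol 8.1.2 pairs those weeks with a dose count that does not match them

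*SAP*

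**What the plan says.** **SAP.** Section 1.5 says the plan rests on a protocol dated 27 July 2018. Section 1.4 lists "An up to 120-week Extension Treatment Period (ETP"), and section 2.1.3.8 repeats the length: "During the 120-week extension period, pre-infusion samples from all patients will be collected every 3 months". Total time in the study appears in section 1.1 ("follow-up in the Extension Period for up to a total of 3 years in the study") and section 3 ("While all patients will be followed for up to 3 years during the study"). Table 5 in section 2.5.4 has its last efficacy window at Week 145. On closing the study, section 2 says "A final DBL will occur and a final CSR will be prepared after the ETP analyses", and section 4 says "The final database lock for the study is planned to be approximately 30 days after the last patient last visit in ETP".

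**Protocol, duration.** The sentences that match SAP 1.1 and 3 read "follow-up in the Extension Period for up to a total of 7 years in the study" (6.1) and "While all patients will be followed for up to 7 years during the study" (11.5). Section 6.2.1 lists the 120-week extension and a long-term period of up to 226 weeks, or until approval, as two separate items. Section 6.2.2 ends the trial at the last patient's last follow-up contact. Section 8.1 describes one extension of up to 346 weeks. Section 17.4 dates amended protocol 01 to 27 July 2018 and places the added 226 weeks in amended protocol 02, of March 2020.

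**Protocol, doses.** Section 8.1.2 sets the extra period at up to 226 weeks of every-other-week infusions and, in the same sentence, at up to 72 doses. The graphic in 1.1 gives up to 114 doses for that period. Section 10.1.4.1 lists visits every two weeks from W147 to W371.

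**The concern.** The SAP was not updated when the protocol was extended. Its words for the extension, the length of follow-up and the last efficacy visit all describe a study that finishes near Week 145, yet the same document fixes the final database lock and final clinical study report. Two things are at stake. The lock and report may be triggered while patients are still being treated and assessed. And efficacy data collected under the current protocol after Week 145 would reach the statistician with no rule for assigning them to an analysis visit, in a study of about 20 patients.

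The dose conflict is a separate defect, in the protocol itself: two maxima for one period that cannot both describe the same schedule.

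**Working it through.** **1. Period lengths.** Protocol 6.2.1 and SAP 1.4:
- SAP: 25 + 120 = 145 weeks.
- Protocol: 25 + 120 + 226 = 371 weeks; 120 + 226 = 346, matching protocol 8.1.
- Share of a patient's treatment weeks after Week 145 = (W − 145)/W, where W is the last treatment week. This is 0% if approval ends treatment by Week 145 and at most 226/371 = 61%.

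**2. Study days.** Day of Week w = 7(w − 1) + 1. This reproduces Table 5's own targets: Week 13 = Day 85, Week 25 = Day 169, Week 145 = Day 1009. The Week 145 window closes at 1009 + 83 = Day 1092. (A stray ±84 is printed beside it; read literally, it would move the close to Day 1093.)

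| Assessment after Week 145 | First nominal visit without a window | Day | Days after 1092 |
|---|---|---|---|
| Ventilator use (every 2 weeks) | about Week 157 | 1093 | 1 |
| Eyelid position (every 24 weeks) | Week 169 | 1177 | 85 |
| Motor tests, echocardiography, PFT, 6MWT (every 48 weeks) | Week 193 | 1345 | 253 |

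At most (361 − 169)/24 + 1 = 9 six-monthly visits and (337 − 193)/48 + 1 = 4 yearly visits are affected, plus the end-of-treatment visit.

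**3. Two readings of ETP.**
- *ETP is the SAP's 120 weeks.* The last ETP visit is Week 145. The lock about 30 days later can precede the end of trial in protocol 6.2.2.
- *ETP is the protocol's 346-week extension.* The lock sentence waits for everyone, but SAP 1.1, 1.4, 2.1.3.8 and 3 then misstate the period and Table 5 is incomplete.

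The missing efficacy windows follow under both.

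**4. Doses.** Every-other-week infusions from Week a to Week b = (b − a)/2 + 1. The rule reproduces the protocol's other totals:
- Day 1 (Week 1) to Week 25: (25 − 1)/2 + 1 = 13; stated 13.
- Week 27 to Week 145: (145 − 27)/2 + 1 = 60; stated 60.

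Applied to the long-term period:
- Week 147 to Week 371: (371 − 147)/2 + 1 = 113.
- The printed visit list omits W355: 104 visits (W147–W353) + 8 (W357–W371) = 112.
- 72 doses: 72 × 2 = 144 weeks, with the last dose at Week 147 + 2 × 71 = 289. That is 113 − 72 = 41 infusions and 371 − 289 = 82 weeks short of the full schedule.

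**The case against.** The strongest reply is that the lock is tied to an event, not a date, and that protocol 8.1 divides the study into 25 weeks and up to 346 weeks, which maps naturally onto the SAP's PAP and ETP. SAP 2.1.3 and 2.4.3.1 also end the extension at the last dose, with no week limit. This stands as far as it goes: the lock sentence is not wrong in itself, and it would be too strong to say that the lock will be early. But it rescues that sentence only by contradicting the SAP's stated period lengths, and it supplies no windows.

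Second, SAP 3 calls analyses after the PAP supportive, and the long-term period was added so that patients could continue treatment. That limits the weight of the point but does not remove it, because the protocol still schedules efficacy assessments there.

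Third, CK. A reader might infer that late CK values have no visit rule at all. They do: safety laboratory tables use the nominal visit (SAP 2.5.4). Only the efficacy table for CK lacks a window. The ventilator figure is also approximate, since it turns on one day and Table 5 assigns by actual date.

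Fourth, all the dose figures are maxima and approval may end treatment sooner. That does not reconcile two maxima for the same period. A reader might link 72 doses (144 weeks) to the UK limit of 144 weeks in protocol 17.3.1.2, but that limit runs from enrolment of the last patient and 8.1.2 does not tie the 72 to it.

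Fifth, a reader might infer that the dose conflict changes who is flagged as non-compliant. The documents do not support this. It requires the SAP's extension to include Week 147 onwards, which is the opposite of the reading that makes the lock early. SAP 2.4.3.2 does not say how the expected amount is derived, and it also flags anyone who misses two or more consecutive infusions.

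**Conclusion.** Both conflicts hold and should be corrected; neither touches the Week 25 primary analysis.

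*SAP.* The plan follows the protocol of 27 July 2018. Its label of Amendment 03 might suggest the current amended protocol 03, but the date is that of amended protocol 01. An early final lock and report is possible under the SAP's own ETP definition, not certain. The absence of efficacy windows after Day 1092 holds under either definition. How much data this concerns depends on approval dates, which are not in the documents, and UK patients have a separate limit; the range is 0% to 61% of a patient's treatment weeks. A reader might infer that late safety data are lost as well. They are not: the safety epochs run to 4 weeks after the last dose (reducible to 2 weeks in stated cases), and laboratory, ECG and vital-sign tables use nominal visits.

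*Protocol.* For one period the documents give 72, 112, 113 and 114 infusions by statement or by count. The difference between 113, 114 and the listed 112 is a slip of one or two; 72 is 41 below the schedule. Which figure is intended cannot be settled from the documents and is not for this review to say.

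**What to change.** **SAP.** Amend sections 1.1, 1.4, 1.5, 2, 2.1.3.8, 3, 4 and Table 5 to:
- cite the current protocol;
- state whether ETP, or a newly named period, covers Week 147 onwards;
- add efficacy windows for the later 12-, 24- and 48-week and end-of-treatment assessments, including ventilator use and CK as an efficacy endpoint;
- tie the final lock and final report to the end of trial in protocol 6.2.2.

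The safety epoch and exposure rules need only the clear period definition. An interim analysis at Week 145 is optional.

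**Protocol.** Reconcile the duration and dose count in 8.1.2, the dose count in the 1.1 graphic and the visit list in 10.1.4.1, including the omitted W355. SAP 2.4.3.2 need use the reconciled count only if its extension period is defined to include Week 147 onwards.

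**Cost.** One SAP amendment, and a protocol correction through the usual approvals (protocol section 15). No new data collection. The price is a later final lock and final report, which an interim could offset.

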5 SOFTWARE DOCUMENTATION

All summaries and statistical analyses will be generated using SAS version 9.4 or higher.

7 LIST OF APPENDICES

[Appendix A](#): Classification of changes (including improvement, unchanged or worsening) from baseline to Week 25 for the 3 domains comprising the composite score

[Appendix B](#) Potentially clinically significant abnormalities (PCSA) criteria

Appendix A Classification of changes (including improvement, unchanged or worsening) from baseline to Week 25 for the 3 domains comprising the composite score (9).

Parameter	Baseline	Week 25		
		Improvement	Unchanged	Worsening
Respiratory	No use of any ventilation assistance	NA	No use of any ventilation assistance	Use of any ventilation assistance
	Use non-invasive ventilation assistance during daytime only or nighttime only	No use of any ventilation assistance	Use non-invasive ventilation assistance during daytime only or nighttime only	Use non-invasive ventilation assistance during both daytime and nighttime Use invasive ventilation assistance
	Use non-invasive ventilation assistance during both daytime and nighttime	No use of any ventilation assistance Use non-invasive ventilation assistance during daytime only or nighttime only	Use non-invasive ventilation assistance during both daytime and nighttime	Use invasive ventilation assistance
	Use invasive ventilation assistance during daytime only or nighttime only	No use of any ventilation assistance Use non-invasive ventilation assistance	Use invasive ventilation assistance during daytime only or nighttime only	Use invasive ventilation assistance during both daytime and nighttime
	Use invasive ventilation assistance during both daytime and nighttime	No use of any ventilation assistance Use non-invasive ventilation assistance Use invasive ventilation assistance <24 hrs/day	Use invasive ventilation assistance during both daytime and nighttime	NA
Motor Skills: GMFM-88 Total Score ^a	Level I Walker	Total Score increase ≥ 3.22	$-3.22 < \text{Total Score change} < 3.22$	Total Score decrease ≥ 3.22
	Level II Supported walker	Total Score increase ≥ 2.76	$-2.76 < \text{Total Score change} < 2.76$	Total Score decrease ≥ 2.76
	Level III Supported stander	Total Score increase ≥ 1.41	$-1.41 < \text{Total Score change} < 1.41$	Total Score decrease ≥ 1.41
	Level IV Sitter	Total Score increase ≥ 1.65	$-1.65 < \text{Total Score change} < 1.65$	Total Score decrease ≥ 1.65
	Level V Restricted antigravity movement	Total Score increase ≥ 0.8	$-0.8 < \text{Total Score change} < 0.8$	Total Score decrease ≥ 0.8
Presence of Ptosis	No ptosis	NA	No ptosis	≥ 1 eye has ptosis
	1 eye only	No ptosis	1 eye only	Both eyes
	Both eyes	≤ 1 eye has ptosis	Both eyes	NA

a. - Total score is Total percent score of GMFM-88, and baseline of Level I-V are GMFCS Levels

Appendix B Potentially clinically significant abnormalities criteria

Measures	Adult Criteria	Pediatric Criteria
Liver function tests		
ALT	>3 x ULN	$\geq 3 \times \text{ULN}$
	>5 x ULN	$\geq 5 \times \text{ULN}$
	>10 x ULN	$\geq 10 \times \text{ULN}$
	>20 x ULN	$\geq 20 \times \text{ULN}$
AST	>3 x ULN	$\geq 3 \times \text{ULN}$
	>5 x ULN	$\geq 5 \times \text{ULN}$
	>10 x ULN	$\geq 10 \times \text{ULN}$
	>20 x ULN	$\geq 20 \times \text{ULN}$
Alkaline Phosphatase	>1.5 x ULN	$\geq 1.5 \times \text{ULN}$
Total Bilirubin	>1.5 x ULN	$\geq 1.3 \times \text{ULN}$
	>2 x ULN	
ALT and Total Bilirubin	ALT >3 x ULN and Total Bilirubin >2 x ULN	ALT $\geq 3 \times \text{ULN}$ and Total Bilirubin $\geq 2 \times \text{ULN}$
Hematology		

White Blood Cell (WBC)	<3.0 GIGA/L (non-Black), <2.0 GIGA/L (Black), ≥16.0 GIGA/L	Birth/0 to 27 days old (Neonates) <4.0 GIGA/L >25.0 GIGA/L 28 days/1 month to 23 months old (Infants) <4.0 GIGA/L >20.0 GIGA/L 24 months/2 years to <6 years old (Children) >3.0 GIGA/L >16.0 GIGA/L 6 to <12 years old (Children) <5.0 GIGA/L >17.0 GIGA/L 12 to 16/18 years old (Adolescents) <4.5 GIGA/L >13.5 GIGA/L
Lymphocytes	>4.0 GIGA/L	Birth/0 to 27 days old (Neonates) <1.2 GIGA/L >17.0 GIGA/L 28 days/1 month to 23 months old (Infants) <2.0 GIGA/L >13.5 GIGA/L 24 months/2 years to <6 years old (Children) <1.0 GIGA/L >9.5 GIGA/L 6 to <12 years old (Children) <1.0 GIGA/L >8.0 GIGA/L 12 to 16/18 years old (Adolescents) <0.6 GIGA/L >6.0 GIGA/L

Neutrophils	<1.5 GIGA/L (non-Black) <1.0 GIGA/L (Black)	Birth/0 to 27 days old (Neonates) <4.0 GIGA/L (1 day old) <1.5 GIGA/L (2 – 7 days old) <1.25 GIGA/L (>7 day – 1 month old) >1 ULN 28 days/1 month to 23 months old (Infants) <1.0 GIGA/L (1 – 3 months) <1.2 GIGA/L (3 – 24 months) >1 ULN 24 months/2 years to <6 years old (Children) <1.2 GIGA/L >1 ULN 6 to <12 years old (Children) <1.2 GIGA/L >1 ULN 12 to 16/18 years old (Adolescents) <1.2 GIGA/L >1 ULN
Monocytes	>0.7 GIGA/L	
Basophils	>0.1 GIGA/L	
Eosinophils	>0.5 GIGA/L or >ULN if ULN \geq 0.5 GIGA /L	>0.5 GIGA/L Or >ULN if ULN $>$ 0.5 GIGA/L
Hemoglobin	Males: \leq 115 g/L (\leq 7.14 mmol/L), \geq 185 g/L (\geq 11.48 mmol/L) Females: \leq 95 g/L (5.9 mmol/L), \geq 165 g/L (10.24 mmol/L) Decrease from Baseline \geq 20 g/L (1.24 mmol/L)	Birth/0 to 27 days old (Neonates) <86 mmol/L or 12.0 g/dL or any decrease $>$ 0.31 mmol/L or 2 g/dL 28 days/1 month to 23 months old (Infants) <1.40 mmol/L or 9.0 g/dL or any decrease $>$ 0.31 mmol/L or 2 g/dL 24 months/2 years to <16/18 years old (Children, Adolescents) <1.55 mmol/L or 10.0 g/dL or any decrease $>$ 0.31 mmol/L or 2 g/dL

Hematocrit	Males : ≤ 0.37 v/v, ≥ 0.55 v/v Females : ≤ 0.32 v/v, ≥ 0.5 v/v	Birth/0 to 27 days old (Neonates) <0.39 l/l or 40% >0.61 l/l or 47% 28 days/1 month to 23 months old (Infants) <0.29 l/l or 29% >0.42 l/l or 42% 24 months/2 years to <16/18 years old (Children, Adolescents) <0.32 l/l or 32% >0.47 l/l or 47%
RBC	≥ 6 TERA/L	
Platelets	<100 GIGA/L and 20% decrease from baseline ≥ 700 GIGA/L is missing	<100 GIGA/L >700 GIGA/L

ECG – PCSA criteria

HR	<50 bpm	Birth/0 to 27 days old (Neonates)
	<50 bpm and decrease from baseline ≥ 20 bpm	≤ 90 bpm and decrease from baseline ≥ 20 bpm
	<40 bpm	≥ 190 bpm and increase from baseline
	<40 bpm and decrease from baseline ≥ 20 bpm	≥ 20 bpm
	<30 bpm	28 days/1 month to 23 months old (Infants)
	<30 bpm and decrease from baseline ≥ 20 bpm	≤ 80 bpm and decrease from baseline
		≥ 20 bpm
		≥ 175 bpm and increase from baseline
		≥ 20 bpm
	>90 bpm	24 months/2 years to <6 years old (Children)
	>90 bpm and increase from baseline ≥ 20 bpm	≤ 75 bpm and decrease from baseline
	>100 bpm	≥ 20 bpm
	>100 bpm and increase from baseline ≥ 20 bpm	≥ 140 bpm and increase from baseline
	>120 bpm	≥ 20 bpm
	>120 bpm and increase from baseline ≥ 20 bpm	6 to <12 years old (Children)
		≤ 50 bpm and decrease from baseline
		≥ 20 bpm
		≥ 120 bpm and increase from baseline
		≥ 20 bpm
		12 to 16/18 years old (Adolescents)
		≤ 50 bpm and decrease from baseline
		≥ 20 bpm
		≥ 120 bpm and increase from baseline
		≥ 20 bpm
PR	>200 ms	Birth/0 to 27 days old (Neonates) ≥ 120 ms
	>200 ms and increase from baseline $\geq 25\%$	28 days/1 month to 23 months old (Infants) ≥ 140 ms
	> 220 ms	24 months/2 years to <6 years old (Children) ≥ 160 ms
	>220 ms and increase from baseline $\geq 25\%$	6 to <12 years old (Children) ≥ 170 ms
	> 240 ms	12 to 16/18 years old (Adolescents) ≥ 180 ms
	> 240 ms and increase from baseline $\geq 25\%$	

QRS	>110 ms	Birth/0 to 27 days old (Neonates) \geq 85 ms
	>110 msec and increase from baseline \geq 25%	28 days/1 month to 23 months old (Infants) \geq 85 ms
	>120 ms	24 months/2 years to <6 years old (Children) \geq 95 ms
	>120 ms and increase from baseline \geq 25%	6 to <12 years old (Children) \geq 100 ms
QTc (either QTcF or QTcB)	Absolute values (ms)	Birth/0 to <12 years old (Neonates, Infants, Children)
	>450 ms	Absolute values (ms)
	>480 ms	Borderline: 431 – 450 ms
	>500 ms	Prolonged*: >450 ms Additional: \geq 500 ms
	Increase from baseline	AND
	30-60 ms	Increase from baseline
	>60 ms	Borderline: Increase from baseline 30 – 60 ms Prolonged*: Increase from baseline >60 ms
		12 to 16/18 years old (Adolescents)
		Absolute values (ms)
		Borderline: 431 – 450 ms (Boys);451 – 470 ms (Girls) Prolonged*: >450 ms (Boys);>470 ms (Girls) Additional: \geq 500 ms
		AND
		Increase from baseline
		Borderline: Increase from baseline30 – 60 ms Prolonged*: Increase from baseline >60 ms

*QTc prolonged and Δ QTc >60 ms are the PCSA to be identified in individual subjects/patients listings.

Clinical chemistry

Creatinine	\geq 150 μ mol/L (Adults)	Birth/0 to <6 years old (Neonates, Infants, Children)
	\geq 30% increase from baseline	$>53 \mu$ mol/L or 0.6 mg/dL
	\geq 100% increase from baseline	6 years to <12 years old (Children)
Urea	\geq 100 μ mol/L (Adults)	\geq 90 μ mol/L or 1.1 mg/dL
	\geq 30% increase from baseline	12 years to 16/18 years old (Adolescents)
	\geq 100% increase from baseline	\geq 132 μ mol/L or 1.5 mg/dL

Blood Urea Nitrogen	≥ 17 mmol/L	Birth/0 to 27 days old (Neonates) ≥ 4.3 mmol/L or 12 mg/dl 28 days/1 month to 16/18 years old (Infants, Children, Adolescents) ≥ 6.4 mmol/L or 18 mg/dl
Chloride	<80 mmol/L >115 mmol/L	≤ 80 mmol/L ≥ 115 mmol/L
Sodium	≤ 129 mmol/L ≥ 160 mmol/L	≤ 129 mmol/L ≥ 150 mmol/L
Potassium	<3 mmol/L ≥ 5.5 mmol/L	Birth/0 to 27 days old (Neonates) ≤ 3.0 mmol/L ≥ 7.0 mmol/L 28 days/1 month to 23 months old (Infants) ≤ 3.5 mmol/L ≥ 6.0 mmol/L 24 months/2 years to 16/18 years old (Children, Adolescents) ≤ 3.5 mmol/L ≥ 5.5 mmol/L
Glucose		
Hypoglycemia	≤ 3.9 mmol/L and $<LLN$	<2.7 mmol/L
Hyperglycemia	≥ 11.1 mmol/L (unfasted); ≥ 7 mmol/L (fasted)	≥ 7 mmol/L (fasted after >12 hours of fast); ≥ 10.0 mmol/L (unfasted)
Albumin	≤ 25 g/L	
Vital signs		

Heart rate	≤ 50 bpm and decrease from baseline ≥ 20 bpm ≥ 120 bpm and increase from baseline ≥ 20 bpm	Birth/0 to 27 days old (Neonates) ≤ 90 bpm and decrease from baseline ≥ 20 bpm ≥ 190 bpm and increase from baseline ≥ 20 bpm 28 days/1 month to 23 months old (Infants) ≤ 80 bpm and decrease from baseline ≥ 20 bpm ≥ 175 bpm and increase from baseline ≥ 20 bpm 24 months/2 years to <6 years old (Children) ≤ 75 bpm and decrease from baseline ≥ 20 bpm ≥ 140 bpm and increase from baseline ≥ 20 bpm 6 to <12 years old (Children) ≤ 50 bpm and decrease from baseline ≥ 20 bpm ≥ 120 bpm and increase from baseline ≥ 20 bpm 12 to 16/18 years old (Adolescents) ≤ 50 bpm and decrease from baseline ≥ 20 bpm ≥ 120 bpm and increase from baseline ≥ 20 bpm
Systolic BP	≤ 95 mmHg and decrease from baseline ≥ 20 mmHg ≥ 160 mmHg and increase from baseline ≥ 20 mmHg	Birth/0 to 27 days old (Neonates) ≤ 60 mmHg and decrease from baseline ≥ 20 mmHg ≥ 85 mmHg and increase from baseline ≥ 20 mmHg 28 days/1 month to 23 months old (Infants) ≤ 70 mmHg and decrease from baseline ≥ 20 mmHg ≥ 98 mmHg and increase from baseline ≥ 20 mmHg 24 months/2 years to <6 years old (Children) ≤ 70 mmHg and decrease from baseline ≥ 20 mmHg ≥ 101 mmHg and increase from baseline ≥ 20 mmHg 6 to <12 years old (Children) ≤ 80 mmHg and decrease from baseline ≥ 20 mmHg ≥ 108 mmHg and increase from baseline ≥ 20 mmHg 12 to 16/18 years old (Adolescents) ≤ 90 mmHg and decrease from baseline ≥ 20 mmHg ≥ 119 mmHg and increase from baseline ≥ 20 mmHg

Diastolic BP	≤ 45 mmHg and decrease from baseline ≥ 10 mmHg ≥ 110 mmHg and increase from baseline ≥ 10 mmHg	Birth/0 to 27 days old (Neonates) ≤ 34 mmHg and decrease from baseline ≥ 10 mmHg ≥ 50 mmHg and increase from baseline ≥ 10 mmHg 28 days/1 month to 23 months old (Infants) ≤ 34 mmHg and decrease from baseline ≥ 10 mmHg ≥ 54 mmHg and increase from baseline ≥ 10 mmHg 24 months/2 years to <6 years old (Children) ≤ 34 mmHg and decrease from baseline ≥ 10 mmHg ≥ 59 mmHg and increase from baseline ≥ 10 mmHg 6 to <12 years old (Children) ≤ 48 mmHg and decrease from baseline ≥ 10 mmHg ≥ 72 mmHg and increase from baseline ≥ 10 mmHg 12 to 16/18 years old (Adolescents) ≤ 54 mmHg and decrease from baseline ≥ 10 mmHg ≥ 78 mmHg and increase from baseline ≥ 10 mmHg
--------------	---	--

Signature Page for VV-CLIN-0258347 v2.0
act14132-16-1-9-sap

Approve & eSign

